4.2 Outcome Variables/Endpoints

In Phase 1, there are no outcome variables/endpoints.

4.2.1 Primary Outcome Variables/Endpoints

In Phase 1, this is not applicable.

In Phase 2, the primary outcomes are patient portal use (number of logins over past 3 months) and glycosylated hemoglobin (A1C).

4.2.2 Secondary and Exploratory Outcome Variables/Endpoints (if applicable)

In Phase 1, this is not applicable.

In Phase 2, secondary outcomes include: a) patient engagement with care (clinic appointments, referrals, ER visits, hospitalizations, use of community resources for social determinants of health); b) T2D clinical management (EMR data of A1C, blood pressure, lipid profile, BMI); c) T2D self-management (medication, blood glucose monitoring, healthy eating, physical activity); d) psychosocial outcomes (diabetes self-efficacy, autonomy support, and diabetes distress); e) technology outcomes (digital literacy, acceptance/use/confidence); and f) satisfaction.

We will also collect data on the intervention implementation which will be assessed by data on the sequence and timing of sessions, # of rescheduled/reminders for sessions, and how the portal was used by patients, CHWs, nurses, and providers. Implementation will also be measured via treatment fidelity. Lastly, we will use data from all field notes of trainings and meetings with interventionists to determine barriers and facilitators to implementation.

5 Study Participants

5.1 Study Population

Phase 1: Participants with T2D diagnosed with T2D for at least 6 months aged 18 years or older, of diverse race/ethnicity, who access healthcare at CHCs. We will seek variability with respect to age, gender, race/ethnicity, and duration of T2D. Participants will be recruited from an outpatient setting – CHCs.

We will also recruit healthy health care providers who provide care for adults with T2D at CHCs.

Phase 2: Participants with T2D diagnosed with T2D for at least 6 months aged 18 years or older, of diverse race/ethnicity, who access healthcare at CHCs. We will seek variability with respect to age, sex, race/ethnicity, and duration of T2D. Participants will be recruited from outpatient settings – Fair Haven and Norwalk CHCs. These are the same CHCs we worked with in Phase 1.

5.2 Number of Participants

For Phase 1, we will recruit health care providers (n=5), CHWs, (n=2), and adults with T2D (n=5), at each clinical site (total sample: 10 providers, 4 CHWs, and 10 adults with T2D).

For Phase 2, we will recruit 30 adults with T2D (n=15 from each clinic).

5.3 Eligibility Criteria

Phase 1 eligibility criteria for adults with T2D

In order to be eligible for inclusion in the study, an individual must meet all of the following criteria:

- Established patient of one of the partner CHCs;
- Age ≥ 18 years;
- Diagnosed with T2D ≥ 6 months;
- Able to read in English or Spanish.

Any individual who meets any of the following criteria will be excluded from participation in this study:

Cognitive impairment (≥ 3 errors on the Six Item Screener for cognitive impairment in clinical research [SIS]) (Callahan et al. 2002) as they will have difficulty in completing the study requirements

Gestational diabetes

Diagnosis of type 1 diabetes

Phase 1 eligibility criteria for health care providers

In order to be eligible for inclusion in the study, an individual must meet all of the following criteria:

Health care provider or community health worker at one of our partner CHC

Provides care/services for adults with T2D

Any individual who meets any of the following criteria will be excluded from participation in this study:

None

Vulnerable/special populations that will be included are: economically or educationally disadvantaged populations and elderly populations (who do not demonstrate cognitive impairment). These groups have health disparities with respect to patient portal use and are important to include in the research to be able to address their needs and improve health equity and health outcomes.

Phase 2: Inclusion criteria are: established patient of one of the partner CHCs; age 18 years or older; diagnosed with T2D >6 months; most recent A1C >7.5%; no current use of patient portal, no intention of moving/changing clinic within 6 months; and able to read in English or Spanish. Exclusion criteria include: cognitive impairment and gestational diabetes.

Participants who participated in Phase 1 will be eligible to participate in Phase 2.

Vulnerable/special populations that will be included are: economically or educationally disadvantaged populations and elderly populations (who do not demonstrate cognitive impairment). These groups have health disparities with respect to patient portal use and are important to include in the research to be able to address their needs and improve health equity and health outcomes.

5.4 Recruitment Procedures

Phase 1:

We will use convenience and purposive sampling through flyers at clinics, in-person recruitment by research assistants (RAs), social media advertisements at clinics, and recommendations from clinic leadership and participants.

For providers, we will use convenience and purposive sampling to achieve variation in type of provider (e.g. MD or NP), age, gender, and race/ethnicity. For CHWs, we will seek diversity in years at CHC, gender, and race/ethnicity. For adults with T2D, we will also use convenience and purposive sampling to achieve variation in use of portals (never users, occasional users, frequent users) as well as variation in age, gender, race/ethnicity, and duration of T2D.

Interested participants will be invited to contact the research team to obtain more information about the study. At the first contact, a trained research assistant will determine eligibility using an established script. If eligible and interested, the research assistant will inform the person about the study procedures and schedule an appointment for the informed consent. If not eligible or interested, the participant will be thanked for their time.

Ideally, we will conduct focus groups in-person if safe to do so, or via Zoom. If an eligible and interested participant can not make the focus group interview time, we will schedule an individual interview in-person (if safe to do so) or via zoom, depending on participant preference. Providers will not complete interviews during work hours. Interviews will be scheduled at lunch, in the evening, or other times that the employee is not working at the clinic.

Phase 2: We will use convenience and purposive sampling through flyers at clinics, in-person recruitment by clinic personnel, social media advertisements at clinics, and recommendations from clinic leadership and participants.

Recruits who express an interest in the study will be invited to contact a language-concordant member of the research team to obtain more information about the study. At this contact, an IRB-approved trained consentor will determine eligibility using an established script. If eligible and interested, the research assistant will inform the recruit about the study procedures and schedule an appointment for the informed consent. If not eligible or interested, the recruit will be thanked for their time. If eligible and interested, the recruit will move on to the consent procedure.

5.5 Consent/Accent Procedures/HIPAA Authorization

Phase 1:

- Consent forms describing in detail the study intervention, study procedures, and risks are sent electronically or given to the participant and written, electronic, or audio-recorded verbal documentation of informed consent is required prior to starting procedures/administering study intervention.
- Consent forms will be Institutional Review Board (IRB)-approved. A trained research assistant will explain the research study to the participant and answer any questions that may arise. This conversation will take place in a private room.
- Participants will have the opportunity to carefully review the written consent form and ask questions prior to signing. The participants should have the opportunity to discuss the study with their family or surrogates or think about it prior to agreeing to participate.
- Participants must be informed that participation is voluntary and that they may withdraw from the study at any time, without prejudice. A copy of the informed consent document will be given to the participants for their records.
- A verbal explanation will be provided in terms suited to the participant's comprehension of the purposes, procedures, and potential risks of the study and of their rights as research participants.
- Prior to the focus group or interview with patient participants, informed consent will be obtained by a trained research assistant. Participants will be asked if they prefer

to read the informed consent or have the informed consent document read to them. If done via Zoom, participants will be asked if they want to read the informed consent document that was sent to them electronically prior to the Zoom meeting or if they would prefer to have the research assistant share the informed consent document on the screen. The research assistant will paraphrase key sections, answer any questions, assure understanding by asking participants to state their understanding of the study procedures, and obtain written, electronic, or audio-recorded verbal informed consent based on patient preference. If patients prefer to complete the informed consent process remotely, we will send a copy of the informed consent via mail or electronically. We will then send the patient participant a link to a secure Zoom meeting. At this Zoom meeting, the research assistant will follow the aforementioned procedure to obtain informed consent. We will provide patients with the option to audio record the review of the last paragraph of the informed consent and ask patients to state if they consent to the study or to send them a link to an electronic survey in Qualtrics that they can read the last paragraph of the informed consent with options to 'agree' or 'not agree' to participation.

For interviews with healthcare providers that are conducted in person or over Zoom, we will provide them with a copy of the informed consent document via email prior to the interview and obtain verbal consent prior to the actual interview.

Phase 2:

- Consent forms (English or Spanish) describing in detail the study intervention, study procedures, and risks will be sent electronically to the recruit or handed to them on paper. The choice of in-person or electronic will be determined by recruit preference. Written, electronic, or audio-recorded verbal documentation of informed consent will be obtained prior to starting procedures/administering study intervention.
- Consent forms will be Institutional Review Board (IRB)-approved. A trained and IRB-approved RA (fluent in Spanish for Spanish speaking recruits) will explain the research study to the recruit and answer any questions that may arise. This conversation will take place in a private room/setting.
- Recruits will have the opportunity to carefully review the written consent form and ask questions prior to signing. They will have the opportunity to discuss the study with their family or surrogates or think about it prior to agreeing to participate.
- Recruits will be informed that participation is voluntary and that they may withdraw from the study at any time, without prejudice. A copy of the informed consent document will be given to the participants for their records.
- A verbal explanation will be provided in terms suited to the participant's comprehension of the purposes, procedures, and potential risks of the study and of their rights as research participants.

- Prior to baseline data collection, informed consent will be obtained by a trained RA. Recruits will be asked if they prefer to read the informed consent or have the informed consent document read/paraphrased. If done via Zoom, participants will be asked if they want to read the informed consent document that was sent to them electronically prior to the Zoom meeting or if they would prefer to have the RA share the informed consent document on the screen. The RA will paraphrase key sections, answer any questions, assure understanding by asking participants if they have any questions, and obtain written, electronic (Qualtrics), or audio-recorded verbal informed consent based on patient preference.

6 Study Methods/Procedures

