The World Health Organization (WHO) *Social Determinants of Health Equity* provides a useful framework for reducing disparities in patient portal use. It posits that socioeconomic position produces health disparities through four intermediary factors - material circumstances, psychosocial factors, behavioral/biological factors, and the healthcare system. We will develop and evaluate a multi-level intervention aimed at increasing access and use of patient portals for diabetes management (*MAP*) in community health centers (CHCs). *MAP* will intervene on each intermediary factor of the WHO framework. Specifically, *MAP* will: 1) provide free access to tablets and internet (material circumstances); 2) deliver technology training and support (psychosocial factors); 3) assess social determinants of health and refer to community resources (material circumstances); and, 4) provide diabetes self-management support and referral to clinic services (behavioral/biological factors). *MAP* will be delivered by community health workers and nurses already embedded in CHCs' healthcare system. Intervention components will be tailored for low-literacy, low-numeracy adults and communications will be designed to increase participant's autonomy for portal use and diabetes self-management. We hypothesize that *MAP* will increase portal use and patient engagement with health care, improve diabetes self-management and psychosocial outcomes, and ultimately improve glycemic control.

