2.2 Risks

For Phase 1 of this study, there are minimal risks. We will collect personal health information from adults with T2D regarding their age, gender, race/ethnicity, type of insurance, duration of T2D, and self-report of most recent A1C (measurement of glycemic control). We will collect information from health care providers and community health workers on age, gender, race/ethnicity, type of healthcare provider and years providing care in a CHC. There is a risk of loss of confidentiality. The study will be conducted in accordance with HIPAA regulations. All study staff will receive certified IRB training and will sign a confidentiality agreement. Strict safeguards will be in place to ensure the confidentiality of the data. Confidentiality will be protected through coding mechanisms. Each study subject will be given a unique study identification number that will be used on all study forms and data files. Each participant's identifying data will be separated from the study data. The code linking a participant to their code number will be maintained in a separate file on a secure server at Yale (eg. Secure Box). All identifying information will be destroyed at the earliest possible time following completion of the study. Results from this investigation will be reported in aggregate, with no potential for individual patients to be identified.

For Phase 2 of this study, there are minimal risks. We will collect personal health information from adults with T2D that includes demographic, clinical, behavioral, and psychosocial data. There is a risk of loss of confidentiality. All practices completed in Phase 1 to decrease this risk will be followed in Phase 2. All participants will participate in an intervention that includes education and support on how to log in and use the patient portal and nurse coaching on diabetes self-management via the patient portal. There is a slight risk of hypoglycemia if diabetes self-management is improved; however, all participants will be receiving the nurse coaching by a nurse from the clinic in which they receive medical care and all patients will be

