continue to be followed by their primary care provider for the duration of the study. Nurses will assess for depressive symptoms at their initial session with participants using the PHQ-2. Participants will be informed of a positive screen and advised to contact their primary care provider or behavioral health professional. Primary care providers will also be informed of a positive screen. Nurses will be in communication with primary care providers for any concerns regarding the health status of study participants and all participants will be advised that communications with the nurse on the patient portal are for non-urgent medical concerns. Both patient portals specify that communication with providers is for non-urgent medical questions.

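### Phase 2 consent replaces the Phase 1 state-it-back check with a question that cannot show whether the recruit has understood

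*Combined protocol and SAP*

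**What the plan says.** Section 5.5 describes consent separately for each phase. For Phase 1 patients, the research assistant paraphrases the main sections, answers questions, and is to "assure understanding by asking participants to state their understanding of the study procedures" before consent is recorded. The Phase 2 sentence has the same structure and makes the same claim, but the method becomes "assure understanding by asking participants if they have any questions".

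Section 2.2 labels the two phases alike: "For Phase 1 of this study, there are minimal risks" and "For Phase 2 of this study, there are minimal risks". For Phase 2 it adds a slight risk of hypoglycemia. It also says that all participants will be told that "communications with the nurse on the patient portal are for non-urgent medical concerns", and that both portals carry a similar notice.

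On the population, section 1.1 says: "Intervention components will be tailored for low-literacy, low-numeracy adults". Section 5.3 lists economically or educationally disadvantaged people and the elderly as vulnerable groups to be included. It also requires that Phase 2 recruits can read English or Spanish, and states "Exclusion criteria include: cognitive impairment and gestational diabetes".

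**The concern.** The Phase 2 sentence claims an outcome, understanding, and names a step that cannot deliver it. Asking whether there are questions finds the people who know what they have missed. It does not find those who hold a wrong belief with confidence, or those who are reluctant to ask. The same sentence already has the assistant answering questions, so the named step adds almost nothing.

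The protocol had a better method and gives no reason for leaving it. The change also runs in an unexpected direction, because the check is lighter in the phase where participants agree to more. What is at stake is whether recruits to an intervention built for people with low literacy know what they have agreed to: what will be done, what data will be taken, what the portal is not for, and that they may leave freely.

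**Working it through.** No formula applies, and the plan gives no figure to reproduce. The check is a comparison of the text.

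**Step 1. The two phases side by side.**

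| | Phase 1 (patients) | Phase 2 |
|---|---|---|
| Comprehension step (5.5) | Participant states own understanding of the procedures | Participant is asked whether there are questions |
| What is agreed to (4.1, 6.1, 6.1.1) | One interview or focus group of about 1.5 hours | A 6-month intervention, fingerstick A1C, questionnaires, medical-record data, portal data including message content |
| Named risks (2.2) | Loss of confidentiality | Loss of confidentiality, slight risk of hypoglycemia |
| Risk label (2.2) | Minimal | Minimal |
| Planned adults with T2D (5.2) | 10 | 30 |

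**Step 2. Does another Phase 2 consent step verify understanding?** The remaining Phase 2 text in 5.5 falls into three groups:

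- *Delivering information:* a form in English or Spanish, a copy to keep, an explanation by a trained assistant, a statement that participation is voluntary, the form read aloud or paraphrased, and the bullet beginning "A verbal explanation will be provided in terms suited to the", which promises an explanation pitched at the recruit.
- *Giving opportunity:* time to review, to ask, and to talk with family.
- *Recording the decision:* written, electronic or audio-recorded.

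None of these requires the recruit to show understanding. The Phase 1 list contains the same promise of a suitably pitched explanation and still adds the state-it-back step. So in Phase 1 the protocol did not treat a suitable explanation as a substitute for a check.

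**Step 3. Does a step outside 5.5 do so?**

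- Section 2.2 provides advice to all participants and a portal notice on the non-urgent limit. Both deliver the message. The section does not say when the advice is given, by whom, or how understanding is confirmed.
- Section 6.1 uses teach-back, but after enrolment and to establish technology competence before the participant is connected with the nurse. It is not described as covering consent content or the non-urgent limit.
- Sections 8.2 and 9.3 provide for practice and role play of the consent procedure. These train staff to carry out the step as written. They do not change what the step can detect.

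**Step 4. Result.** The state-it-back check is present in the Phase 1 patient text and absent from the Phase 2 text, and no other step described for Phase 2 takes its place. The Phase 1 check covers study procedures only. Carried over unchanged, it would not clearly test the non-urgent limit, so the fix has to name its content.

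**The case against.** The best case for the plan is that the change in wording does little harm. Both phases are minimal risk by the protocol's own label. The hypoglycemia risk is called slight, and participants are coached by a nurse from their own clinic and stay under their primary care provider. Recruits must be able to read, may have the form read or paraphrased to them, may consult family, and deal with trained staff. Before nurse contact they are expected to have 4-6 one-to-one sessions that include portal use. The consent form, the assistant's script and the intervention appendix are not in the file and may contain more. All of this stands and is why the point is minor. None of it makes a question about questions into a check of understanding.

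A reader might also infer stronger claims, which the documents do not support:

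- *That recruits will enter Phase 2 unaware that the portal is for non-urgent matters.* Section 2.2 gives that message by two routes that do not depend on the consent conversation. What is missing is a stated check that it was understood.
- *That an urgent message would wait days for a nurse who is in touch only once or twice a week.* The frequencies in 6.1 describe the nurse's own outreach: about twice weekly, or as clinically indicated, for 3 months, then weekly. They are not reply times. The protocol states no reply time, so no delay can be derived.
- *That some number of the 30 participants will have misunderstood.* The documents give no comprehension rate, and any count would only restate an assumption.
- *That consent would be invalid.* Section 5.5 says the forms describe procedures and risks in detail. Without the form, its adequacy cannot be judged either way.
- *That Phase 2 consent is also weakened because no cognitive screener is named.* Section 5.3 does exclude cognitive impairment in Phase 2. It omits the instrument and cut-off that Phase 1 gives (three or more errors on the Six Item Screener). That is a gap in an eligibility definition, to be raised separately. Low literacy is not cognitive impairment.

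**Conclusion.** The point holds, as a minor one. The Phase 2 consent sentence names a step that cannot do what it claims, and it is weaker than the protocol's own Phase 1 step for patients. As described, Phase 2 contains no check that recruits understood what they agreed to, including the non-urgent limit that they are to be told about. Phase 2 is the more demanding phase only in relative terms, since both carry the minimal-risk label.

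The size cannot be put in numbers. No endpoint, estimate or sample-size figure is affected, and the effect on comprehension is unknown. The conclusion rests on the protocol text alone and assumes that the unseen script or consent form does not already contain a state-it-back step. If it does, the remedy is simply to make 5.5 say so.

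**What to change.** Reconcile the Phase 1 and Phase 2 text in 5.5 by restoring the state-it-back step for Phase 2. Before consent is taken, the recruit says in their own words what the study procedures are, and three points that the protocol already contains:

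1. Portal messages to the nurse are for non-urgent concerns (2.2).
2. Message content and medical-record data will be collected (6.1.1).
3. Withdrawing does not affect the participant's relationships at the clinic (6.5).

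The assistant re-explains any point stated wrongly and asks for it again before recording consent.

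This goes slightly beyond copying the Phase 1 sentence, because that sentence covers procedures only. The cost is a short revision to 5.5 and the consent script, submitted as an IRB amendment as section 9.1 requires, and a few minutes for each of 30 recruits. It needs no extra staff and changes no endpoint, analysis or clinical procedure.
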